The study treatment solutions must be self-injected subcutaneously in **non-affected** areas of the skin starting with the 2 mL AI, the 2 injections of 1 mL PFS taking place subsequently, after completion of the SIAQ, when applicable. Administration of study treatment may vary on the body regions, i.e., changing the injection site from visit to visit: right thigh, left thigh, right stomach, left stomach, upper outer arm (when assisted by attendant), whilst separating the 2 mL AI and the two 1 mL PFS injection sites. Used syringes and AI should be disposed immediately after use in a sharps container or according to the regulatory needs of the respective countries. More information can be found in the study-specific IFU.

All dates and times of injections during the study must be recorded on the appropriate CRF.

All kits of study treatment assigned by the IRT will be recorded/databased in the IRT.

The investigator must promote compliance by instructing the subject to take the study treatment exactly as prescribed and by stating that compliance is necessary for the subject's safety and the validity of the study. The subject must also be instructed to contact the investigator if he/she is unable for any reason to take the study treatment as prescribed.

7 Informed consent procedures

Eligible subjects may only be included in the study after providing (witnessed, where required by law or regulation), IRB/IEC-approved informed consent.

If applicable, in cases where the subject's representative(s) gives consent (if allowed according to local requirements), the subject must be informed about the study to the extent possible given his/her understanding. If the subject is capable of doing so, he/she must indicate agreement by personally signing and dating the written informed consent document.

Informed consent must be obtained before conducting any study-specific procedures (eg, all of the procedures described in the protocol). The process of obtaining informed consent must be documented in the subject source documents.

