8.4 Safety/Tolerability

Safety assessments are specified below with the assessment schedule detailing when each assessment is to be performed.

Blood withdrawals and safety assessments should be done prior to study treatment administration and should be taken as shown in [Table 8-1](#) and in [Appendix 2](#).

Appropriate safety assessments (eg, evaluation of AEs and SAEs including injection site reactions) should be repeated after the dose is administered. For details on AE collection and reporting, refer to AE section ([Section 10](#)).

Table 8-4 Physical Assessments**Assessment Specification**

Physical examination	A physical examination, including general appearance, skin, neck, eyes, ears, nose, throat, lungs, heart, abdomen, back, lymph nodes, extremities, vascular and neurological systems will be performed as indicated in Table 8-1 . If necessary, based on medical history and/or symptoms, additional exams will be performed at the discretion of the investigator. Whenever possible, assessments for an individual subject should be performed by the same member of the study site staff throughout the study. Information for all physical examinations must be included in the source documentation at the study site. Clinically relevant findings that are present prior to signing informed consent must be included in the Medical History part of the eCRF. Significant findings made after first administration of investigational drug which meet the definition of an AE must be recorded on the Adverse Event section of the eCRF

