2.1.1.3 Screening, baseline and post-baseline definitions

Screening refers to any procedures (e.g., checking inclusion and exclusion criteria) performed prior to the date of first dose of study treatment (for safety analysis) or prior to the randomization date (for efficacy analysis). Per protocol, subject informed consent must be obtained prior to performing any study related activity. The date of signing informed consent is the start date of screening period. Any assessment obtained during the screening period will be labeled screening assessment. Assessments made on Day 1 may occur before or after the randomization or the first dose. Further information will be found in [\[Programming Datasets Specifications \(PDS\)\]](#).

For efficacy analyses, baseline is the last assessment (including unscheduled visits) obtained (on or) before the randomization (day). All assessments obtained after randomization are considered as post-baseline unless otherwise specified.

For safety analyses, baseline is the last assessment (including unscheduled visits) obtained (on or) before the first dose (day) of study treatment. All assessments obtained after the first dose (day) of study treatment are considered as post-baseline unless otherwise specified.

Of note, baseline will be derived based on the randomization day or first dose day, exact randomization/dosing time is not considered.

Of note, re-randomization will not be used for baseline definition and only one baseline value will be defined referring to the first randomization.

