2.4.1.1 Visit window

Visit-windows will be used for the data that is summarized by visit; they are based on the study evaluation schedule and comprise a set of days around the nominal visit day. For any assessment, there are the protocol defined scheduled visits around which visit windows were created to cover the complete range of days within the study. The visit windows are shown in [Table 2-3](#). In this table, the days are counted since the first dose of study treatment (Day 1) for safety assessments, and the days are counted since the date of randomization for efficacy assessments. These visit windows apply to measurements taken at every visit.

When visit windows are used, all visits will be re-aligned, i.e., they will be mapped into one of the visit windows. E.g., if the *Week 4* visit of a subject is delayed and occurs on Day 60 instead of on Day 29, it will be re-aligned to visit window *Week 8*. In the case of major deviations from the visit schedule, or due to unscheduled visits, several assessments of a subject may fall in a particular visit window (either scheduled or unscheduled). Statistical approaches to handle multiple assessments in a given visit window are specified in [Section 2.4.1.2](#).

For parameters which are not collected at every visit (e.g., DLQI), visit windows will be combined. For example, if a parameter is measured at Week 12 and Week 28 only, Week 12 visit window will extend from Day 2 to Day 99 (combining Week 1 to Week 12 visit windows), and Week 28 will extend from Day 100 to Day 239.

Assessments from treatment period 2 will not be considered for treatment period 1, and treatment period 1 visits will not be mapped into treatment period 2.

Table 2-3 Assessment windows for scheduled visits

Analysis Visit	Week	Scheduled Day	Visit Window
Baseline	BSL	1	-28 days to Day 1*
Week 1	1	8	Day 2-11
Week 2	2	15	Day 12-18
Week 3	3	22	Day 19-25
Week 4	4	29	Day 26-43
Week 8	8	57	Day 44-71
Week 12	12	85	Day 72-99
Week 16	16	113	Day 100-155
Week 28	28	197	Day 156-239
Week 40	40	281	Day 240-323
Week 52	52	365	Day 324-421

* Baseline measurement before the first drug administration for safety assessments and before the randomization for efficacy assessments.

Of note: subject's height will not be remapped according to the analysis visit window.

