Table 2-9 CTCAE grades for laboratory parameters to be analyzed

CTCAE v4.0 Term	Grade 1	Grade 2	Grade 3	Grade 4
HGB decreased (Anemia)	<LLN – 100 g/L	<100 – 80 g/L	<80 g/L	Life-threatening consequences; urgent intervention
Platelet count decreased	<LLN – 75.0 x10e9 /L	<75.0 - 50.0 x10e9 /L	<50.0 – 25.0 x10e9 /L	<25.0 x 10e9 /L
White blood cell decreased	<LLN - 3.0 x 10e9 /L	<3.0 - 2.0 x 10e9 /L	<2.0 - 1.0 x 10e9 /L	<1.0 x 10e9 /L
Neutrophil count decreased	<LLN - 1.5 x 10e9 /L	<1.5 - 1.0 x 10e9 /L	<1.0 - 0.5 x 10e9 /L	<0.5 x 10e9 /L
Lymphocyte count decreased	<LLN - 0.8 x 10e9/L	<0.8 - 0.5 x 10e9 /L	<0.5 - 0.2 x 10e9 /L	<0.2 x 10e9 /L
Creatinine increased	>ULN - 1.5 x ULN	>1.5 - 3.0 x ULN	>3.0 - 6.0 x ULN	>6.0 x ULN
TBL increased	>ULN - 1.5 x ULN	>1.5 - 3.0 x ULN	>3.0 - 10.0 x ULN	>10.0 x ULN
GGT increased	>ULN - 2.5 x ULN	>2.5 - 5.0 x ULN	>5.0 - 20.0 x ULN	>20.0 x ULN
ALT increased	>ULN - 3.0 x ULN	>3.0 - 5.0 x ULN	>5.0 - 20.0 x ULN	>20.0 x ULN
AST increased	>ULN - 3.0 x ULN	>3.0 - 5.0 x ULN	>5.0 - 20.0 x ULN	>20.0 x ULN
ALP increased	>ULN - 2.5 x ULN	>2.5 - 5.0 x ULN	>5.0 - 20.0 x ULN	>20.0 x ULN

Shift tables will be presented comparing baseline laboratory result (CTCAE grade) with the worst results (expressed in CTCAE grade) during the treatment phase analyzed. Of note, baseline will be defined as last assessment prior to first dosing in initial treatment phase. If no pre-treatment value exists, also a value recorded after first dose can be used as baseline if it was collected on the same day as first dose, see [Section 2.1.1.3](#).

Exposure time adjusted incidence for subjects with newly occurring neutropenia of CTCAE grade ≥ 2 will be summarized

The number and percentage of subjects with newly occurring liver enzyme abnormalities will also be summarized based on the event criteria given in [Table 2-10](#).

Table 2-10 Liver-related events

Parameter	Criterion
ALT	>3xULN; >5xULN; >8xULN; >10xULN, >20xULN
AST	>3xULN; >5xULN; >8xULN; >10xULN; >20xULN
ALT or AST	>3xULN; >5xULN; >8xULN; >10xULN; >20xULN ALT or AST >3xULN & (nausea or vomiting or fatigue or general malaise or abdominal pain or (rash and eosinophilia))
TBL	>1xULN; >1.5xULN; >2xULN; >3xULN,
ALP	>1.5xULN; >2xULN; >3xULN; >5xULN
ALT or AST & TBL	ALT or AST >3xULN & TBL >1.5xULN; ALT or AST >3xULN & TBL >2xULN; ALT or AST >5xULN & TBL >2xULN; ALT or AST >8xULN & TBL >2xULN; ALT or AST >10xULN & TBL >2xULN; ALT or AST >20xULN & TBL >2xULN;

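### SAP 2.1.1.3 sets the safety baseline by day and ignores dosing time, against the Table 2-3 footnote and SAP 2.8.3, so a post-dose Day 1 vital sign or laboratory value can become baseline (minor)

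*SAP*

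**What the plan says.** The SAP states the safety baseline in three places, and they differ.

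- **SAP 2.1.1.3, general rule.** "For safety analyses, baseline is the last assessment (including unscheduled visits) obtained (on or) before the first dose (day) of study treatment". The section accepts that "Assessments made on Day 1 may occur before or after the randomization or the first dose", refers to the programming specifications for more detail, and then says that "exact randomization/dosing time is not considered". Post-baseline starts a day later: "All assessments obtained after the first dose (day) of study treatment are considered as post-baseline unless otherwise specified".
- **SAP 2.4.1.1, footnote to Table 2-3.** "Baseline measurement before the first drug administration for safety assessments". In the same table the baseline window closes on Day 1 and the Week 1 window runs from Day 2 to Day 11.
- **SAP 2.8.3, in the text on CTCAE shift tables.** "baseline will be defined as last assessment prior to first dosing in initial treatment phase". A value recorded after dosing on the same day may stand in only if there is no pre-treatment value. The section cites 2.1.1.3 for this, but 2.1.1.3 contains no such limit.

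SAP 2.12 applies the same fallback to patient-reported outcomes. SAP 2.8.4.2, on vital signs, uses change from baseline and newly occurring notable values but does not define baseline.

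On timing, Protocol 6.7.2, 8 (order of assessments) and 8.4 place scheduled blood samples, vital signs and safety assessments before the injection. Protocol 8.4 adds that appropriate safety assessments "should be repeated after the dose is administered", giving adverse events and injection site reactions as examples.

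**The concern.** A baseline should describe the subject before exposure. If a post-injection reading becomes the baseline, two things follow for that subject. Every later change from baseline is measured from a value that may already reflect the first dose. An abnormality first seen after that dose is also treated as present at the start, so it drops out of the counts of new or worsening findings.

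An unscheduled Day 1 reading is plausibly taken because the subject felt unwell after the injection, so the affected readings need not be a random sample.

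There is also a reproducibility problem. Two programmers working from this SAP could derive different baselines from the same record, one following 2.1.1.3 and the other the Table 2-3 footnote.

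**Working it through.** The plan gives no figure on this point, so the check is to apply each rule to the possible Day 1 records.

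| Values on record | SAP 2.1.1.3, literal | Table 2-3 footnote | SAP 2.8.3 |
|---|---|---|---|
| Screening, Day 1 pre-dose | Day 1 pre-dose | Day 1 pre-dose | Day 1 pre-dose |
| Screening, Day 1 pre-dose, Day 1 post-dose | **Day 1 post-dose** | Day 1 pre-dose | Day 1 pre-dose |
| Screening, Day 1 post-dose only | **Day 1 post-dose** | Screening | Screening |
| Day 1 post-dose only, nothing earlier | Day 1 post-dose | None (no fallback given) | Day 1 post-dose |

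The conflict sits in rows 2 and 3: a pre-dose value exists and a post-dose Day 1 value exists as well. In row 4, 2.1.1.3 and 2.8.3 agree; the footnote has no fallback of its own.

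**Can the post-dose value count as post-baseline instead?** Not as written. Under 2.1.1.3 post-baseline begins after the first-dose day. Under Table 2-3 no post-baseline window includes Day 1. Table 2-4 selects the most extreme notable value within a window, so a value outside every post-baseline window is not selected.

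**Illustration (an invented record).** Systolic pressure is 124 mmHg pre-dose, 86 mmHg after the first injection and 122 mmHg at Week 1. SAP Table 2-11 treats values below 90 mmHg as notable.

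- SAP 2.1.1.3: baseline 86; Week 1 change 122 − 86 = +36; the value 86 is not counted as new.
- Table 2-3 footnote: baseline 124; Week 1 change 122 − 124 = −2; the value 86 still falls in no post-baseline window, so it is still not counted.

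Choosing the pre-dose baseline therefore repairs the change score but not the count. Counting the 86 needs a further rule that the SAP does not contain.

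**Scale per affected subject.** With about 120 subjects randomized 2:2:1:1 and the two placebo groups pooled up to Week 12, each comparison group has about 40. One subject is 1/40 = 2.5 percentage points in a notable-value table. In the illustration the two change scores differ by 36 − (−2) = 38 mmHg, which moves a group mean by 38/40 = 0.95 mmHg. How many subjects would be affected is not in the documents.

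**What is not affected.** SAP 2.8.1 classes an adverse event as treatment emergent by onset, or increased severity, after the first dose, not by a baseline measurement. Injection site reactions reported as adverse events follow that rule and have their own table. The efficacy baseline is a separate definition tied to randomization.

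**The case against.** The best case for leaving the text alone has four parts.

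1. **Scheduled Day 1 measurements are pre-dose.** This stands. The problem needs a repeat or unscheduled post-dose reading that reaches the database, or a departure from the protocol order. The examples in Protocol 8.4 are adverse events and injection site reactions, and no section schedules a post-dose Day 1 vital sign or blood draw.
2. **The authors probably meant a fallback.** SAP 2.8.3 cites 2.1.1.3 when it limits same-day post-dose values to subjects with no earlier value, and SAP 2.12 does the same. This is likely the intention, but 2.1.1.3 does not say it. For vital signs no section-specific rule corrects it, and the only counterweight is the Table 2-3 footnote.
3. **The programming specifications may settle it.** They may, and they were not available for review. They should not have to override explicit SAP text.
4. **Only descriptive tables are involved.** This stands, and it is why the point is minor.

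A reader might infer more: that a first-dose reaction is in general absorbed into baseline. The documents do not support that, because reactions reported as adverse events are classed by onset. A reader might also take the override of the pre-dose value as the plan's settled rule. It is one of two conflicting rules. Nor does 2.8.3 by itself bring a post-dose Day 1 abnormality into the counts: it covers laboratory data and says nothing about when post-baseline starts.

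**Conclusion.** The contradiction is real and should be removed. SAP 2.1.1.3, read literally, gives the wrong baseline when a subject has a pre-dose value and also a post-dose Day 1 vital sign or laboratory value. It disagrees there with the Table 2-3 footnote and with SAP 2.8.3. Separately, no SAP rule lets such a post-dose value count as post-baseline.

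The reach is narrow: descriptive laboratory and vital-sign summaries, with vital signs most exposed. The co-primary and key secondary analyses, adverse event incidence and injection site reactions reported as adverse events are untouched. The total effect cannot be computed, because the documents give no number or rate of post-dose Day 1 readings; each affected subject weighs at most 2.5 percentage points in a group of 40. That such readings would cluster in subjects who react is plausible but not shown by the documents. Severity: minor.

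**What to change.** Amend SAP 2.1.1.3 as follows and make Table 2-3 and SAP 2.8.3 and 2.8.4.2 refer to it.

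- The safety baseline is the last non-missing value before the first injection, judged by recorded date and time. A scheduled Day 1 value with no time is taken as pre-dose.
- A same-day value known to be post-dose is used only if no pre-treatment value exists. This is the rule already in SAP 2.8.3.
- Other Day 1 values timed after the first injection count as post-baseline in the notable vital-sign and CTCAE tables. This rule would be new to the SAP. It agrees with Protocol 12.6.2, where on-treatment status for the other safety variables starts after the first dose, not after the first-dose day; SAP section 4 lists no change to that.

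The cost is a few sentences and a date-time comparison in programming. The data should be there: "All dates and times of injections during the study must be recorded on the appropriate CRF", and Table 2-4 already uses measurement time to choose between same-day safety values. The one downside is the assumption about untimed scheduled values, which will misplace a reading if a site departed from the protocol order and recorded no time.

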2.1.1.4 Day of last dose of randomized study treatment

The date of last dose will be collected via the CRF. Duration of exposure is defined in [Section 2.4.1](#).

For safety analysis, on-treatment is defined as assessments within last dose plus 84 days.

Of note: study does not have follow up period, the last visit is 4 weeks after last dose.

2.2 Analysis sets

The following analysis sets will be used for the data analysis.

Randomized set: The randomized set will be defined as all subjects who were randomized at baseline visit. Unless otherwise specified, subjects with missing informed consent form as well as mis-randomized subjects will be excluded from the randomized set.

Misrandomized subjects are subjects who are screen-failures, but have been randomized by the investigator before eligibility was finally assessed, however have not been treated. If previously mis-randomized subjects were re-screened and successfully randomized, they will be included in the randomized set according to the treatment assigned in the last randomization.

Full analysis set (FAS): The FAS will be comprised of all subjects from the randomized set to whom study treatment has been assigned. Following the intent-to-treat principle, subjects will be analyzed according to the treatment assigned to at randomization. If the actual randomization stratum is different to the assigned stratum in IRT, the actual stratum will be used in analyses. The subjects with severe GCP violation will not be included in the FAS.

Of note, subjects excluded from the randomized set will be excluded from the FAS.

Safety set: The safety set includes all subjects who took at least one dose of study treatment during the treatment period. Subjects will be analyzed according to treatment received. The treatment received will be set to the treatment randomized. But if a subject has received the wrong treatment during the entire study, the treatment received will be set to this wrong treatment. If a subject has received intermittent wrong treatment, the treatment received will be set to the original randomized treatment.

2.2.1 Subgroup of interest

The co-primary endpoints and important secondary endpoints will be evaluated using the subgroups defined in [Table 2-1](#). Subgroup analyses for the study endpoints are represented in [Table 2-2](#).

Table 2-1 Subgroup definitions

Subgroup variables	Categories	Label for outputs	Suffix for outputs*
Weight category	body weight category (<90 kg, >=90 kg)	Weight category	a

* Suffixes will be used for the outputs numbering, see [\[TFL shell document\]](#)

Table 2-2 Subgroup analyses

Endpoint/analysis	Weight category
Co-primary endpoints:	
PASI 75 response @ Week 12	X
IGA 0/1 response @ Week 12	X
Secondary endpoints:	
PASI 90 response @ Week 12	X
PASI 50/75/90/100 response over time up to week 52	X
IGA 0/1 response over time up to week 52	X

Note: presented are only those endpoints that need subgroup analyses.

2.3 Patient disposition, demographics and other baseline characteristics

The summaries will be shown for the following treatment groups, before or at Week 12:

- AIN457 300 mg (2mL AI), AIN457 300 mg (2x1mL PFS), Placebo, Total after Week 12:
 - AIN457 300 mg (2mL AI), AIN457 300 mg (2x1mL PFS), Placebo, Placebo - AIN457 300 mg (2mL AI), Placebo - AIN457 300 mg (2x1mL PFS), Total

No summaries for entire treatment period will be provided.

The following common background and demographic variables will be analyzed:

Continuous variables:

- Age (which is collected in the RaveX platform directly)
- Height
- Weight
- Body mass index (BMI)

Categorical variables:

- Age categories (<65 years, 65 years and older, 75 years and older)
- Sex
- Race
- Ethnicity
- Smoking status at baseline
- Weight categories (<90 kg, >= 90 kg)

Psoriasis specific baseline characteristics and history of disease will be summarized as well:

Continuous variables:

- Baseline PASI
- Baseline total BSA
- Time since diagnosis of psoriasis
- Time since diagnosis of psoriatic arthritis

Categorical variables:

- Baseline PASI categories (≤ 20 , > 20)
- Baseline IGA mod 2011 score categories (at least mild, moderate, severe)
- Severity of psoriasis categories (CHMP guidelines, mild (total BSA $< 10\%$ and PASI < 10), moderate ((PASI ≥ 10 or total BSA $\geq 10\%$) and PASI ≤ 20 and total BSA $\leq 20\%$), severe (total BSA $> 20\%$ or PASI > 20))
- Baseline psoriatic arthritis categories (yes, no)
- Previous exposure to biologic systemic psoriasis therapy (yes, no)
- Previous exposure to systemic psoriasis therapy (yes, no)

- Previous exposure to non-biologic systemic psoriasis therapy (yes, no)
- Previous failure to biologic systemic psoriasis therapy (yes, no)
- Previous failure to systemic psoriasis therapy (yes, no)
- Previous failure to non-biologic systemic psoriasis therapy (including phototherapy and photo- chemotherapy) (yes, no)

Body Mass Index (BMI) will be calculated using the following formula:

$$\text{BMI} = (\text{body weight in kilograms}) / (\text{height in meters})^2$$

For BMI, height and body weight the last value prior to randomization is used. If there is no weight recorded prior to taking of study treatment, BMI will be missing.

Of note: subject's height will not be remapped according to the analysis visit window.

Time since diagnosis of psoriasis (PsO) and time since diagnosis of psoriatic arthritis (PsA) will be calculated using the following formula:

$$\text{Time since diagnosis} = (\text{inform consent date} - \text{first diagnosis date} + 1) / 365.25$$

The first diagnosis date of PsO or PsA will be imputed according to the imputation rules in [Section 5.1.4](#).

Unless otherwise specified, summary statistics will be presented for continuous variables for each treatment group and for all subjects (total) in the randomized set. The number and percentage of subjects in each category will be presented for categorical variables for each treatment group and all subjects (total) in the randomized set.

Any condition entered on the *relevant medical history / current medical conditions* CRF (including family history) will be coded using the MedDRA dictionary. They will be summarized by System Organ Class (SOC) and Preferred Term (PT) of the MedDRA dictionary.

Summaries for cardiovascular medical history will be summarized by categories.

Smoking history will be summarized by treatment group.

Unless otherwise specified, analyses will be based on the randomized set.

